If a subject decides to be vaccinated with a non-study prophylactic COVID-19 vaccine, either authorized under emergency use or licensed, during the trial, subjects should provide details of the non-study COVID-19 vaccine received to study staff and subjects should be requested to remain in the trial until the last visit. Additionally, subjects should also be advised that we do not have adequate information about the safety and effectiveness of another prophylactic COVID-19 vaccine when received following the receipt of INO-4800. As is already the case, if a subject is enrolled and receives a non-study prophylactic COVID-19 vaccine, either authorized under emergency use or licensed, while on study, the Investigator should enter the details as a concomitant medication. The subject should be followed (according to the Schedule of Events outlined in Table 3 of the Protocol).

Should a subject fail to attend the clinic for a required study visit, the site should attempt to contact the subject and reschedule the missed visit as soon as possible. In cases where the subject does not return for the rescheduled visit or cannot be reached to reschedule the missed visit, the site should make every effort to regain contact with the subject (3 telephone calls and if that fails, then a certified letter to the subject's last known mailing address) so that the subject's disposition can be considered as withdrawn from the study (i.e. lost to follow-up). If the contact with subject is re-established, site should contact medical monitor to discuss whether subject can continue study treatment or follow-up visits for the study. For all other subjects withdrawing from the study, an alternative reason for discontinuation should be recorded in the eCRF.

Reasons for discontinuation/withdrawal from the trial may include but are not limited to the following:

- Subject withdrawal of consent at any time;
- Any medical condition that the Investigator or Sponsor determines may jeopardize the subject's safety if he or she continues in the trial;
- Investigator, DSMB or Sponsor determines it is in the best interest of the subject;
- Subject non-compliance.

INO-4800	COVID19-311
Inovio Pharmaceuticals, Inc.	Clinical Protocol

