Actual or estimated start and stop dates must be provided. This information will be obtained from the subject and/or any available medical records. The indication for the medication, dose, and dose regimen will be documented.

Therapy considered necessary for the subject's welfare may be given at the discretion of the Investigator or medical provider. If the permissibility of a specific medication/treatment is in question, please contact the Medical Monitor.

The decision to administer a prohibited medication/treatment (Section 6.4.7) is made with the safety of the clinical trial subject as the primary consideration. When possible, the Sponsor should be notified before the prohibited medication/treatment is administered.

6.4.7 **RESTRICTIONS**

In the Phase 2 segment of the trial, subjects should refrain from becoming pregnant until 3 months following the last dose of investigational product by using appropriate contraceptive measures (see Section 4.1.1). In the Phase 3 segment of the trial, subjects should refrain from becoming pregnant until receipt of the last dose of investigation product by using appropriate contraceptive measures (See Section 4.1).

Subjects must not receive any non-study related vaccine (e.g., influenza vaccine) within 2 weeks prior to the first dose of IP, or within 2 weeks of (before or after) any subsequent dose of IP.

Subjects must not have fever (oral temperature \geq 38.0 degrees Celsius or 100.4° Fahrenheit) within 72 hours prior to each dosing.

Subjects should not receive hydroxychloroquine during the trial. In the Phase 3 segment, subjects should not receive any other drug/vaccine intended as COVID-19 prophylaxis during the trial. Subjects should be reminded that if and when appropriate, the Sponsor would offer INO-4800 to those who received placebo in the trial if INO-4800 is demonstrated to be efficacious.

For subjects in the Phase 2 segment of the trial, the receipt of any non-study prophylactic COVID-19 vaccine (authorized under emergency use or licensed) is not restricted, based upon increasing availability of EUA vaccine in the US and completion of the Phase 3 dose selection from the Phase 2 data.

If a subject informs the site of their intent to receive a non-study prophylactic COVID-19 vaccine available either authorized under emergency use or when licensed, the subject should be informed that the safety and effectiveness of receiving INO-4800 followed by another COVID-19 vaccine has not been studied.

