8.4 ANALYTICAL POPULATIONS

Analysis populations will be:

The per-protocol (PP) population includes all subjects who receive all doses of Study Treatments and have no protocol violations. Subjects in the PP population will be grouped to treatment arms as randomized. Subjects excluded from the PP population will be identified and documented prior to unblinding of the trial database. Analyses on the PP population among those who are baseline SARS-CoV-2 seronegative will be primary for the analyses of efficacy in the Phase 3 segment of this trial.

The modified intention to treat (mITT) population includes all subjects who receive at least one dose of Study Treatment. Subjects in this population will be grouped to treatment arms as randomized. Analysis of the mITT population will be considered supportive for the corresponding PP population for the analyses of efficacy in the Phase 3 segment of this trial.

The intention to treat (ITT) population includes all subjects who are randomized. Subjects in this sample will be grouped to treatment arms as randomized. Analysis of the ITT population will be considered supportive for the corresponding PP population for the analyses of efficacy in the Phase 3 segment of this trial.

The safety analysis population includes all subjects who receive at least one dose of Study Treatment. Subjects will be analyzed according to the treatments received.

8.5 **DESCRIPTION OF STATISTICAL METHODS**

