8.5.1 PRIMARY ANALYSIS

Phase 2 Segment

Post-baseline increases from baseline in interferon-γ ELISpot response magnitudes will be compared between treatment groups using differences in medians and associated non-parametric 95% CIs.

INO-4800	COVID19-311
Inovio Pharmaceuticals, Inc.	Clinical Protocol

Post-baseline increases from baseline in neutralizing antibody response titers will be compared between treatment groups using ratios of geometric mean fold-rises and associated t-distribution based 95% CIs.

The summaries listed above will be stratified according to NP positive/negative status and according to prior receipt of any non-study prophylactic COVID-19 vaccine of the subjects. Valid samples for statistical analysis purposes will be those collected: at least 6 and no more than 30 days after Dose 2 for the Week 6 timepoint; at least 174 and no more than 198 days after Dose 2 for the Week 30 timepoint; and at least 356 and no more than 380 days after Dose 2 for the Week 56 timepoint. Baseline is defined as the last measurement prior to the first treatment administration.

The PP population will be used for these immunogenicity analyses.

Phase 3 Segment

Among subjects who are SARS-CoV-2 seronegative at baseline, the primary hypothesis of relative efficacy greater than 30% will be tested with H_0 : $p \ge 0.70/(0.70+k)$ vs. H_1 : p < 0.70/(0.70+k), where p is the true proportion of subjects with disease who receive INO-4800 relative to the total number of subjects with disease, and k is the total amount of follow-up time in the placebo group divided by the total amount of follow-up time in the INO-4800 group.

A p-value for this hypothesis test and corresponding confidence interval will be computed based on the exact binomial method of Clopper-Pearson. Success will be concluded if the one-sided p-value is <0.022 and the corresponding lower bound of the two-sided 95.6% Cl for efficacy exceeds 30% (alpha-level adjusted for interim analyses, see Section 8.5.6), and the point estimate for efficacy exceeds 50%.

For calculating k, an individual subject's follow-up time is either:

- the date of first disease diagnosis date of the start of surveillance period +1 (for subjects who are cases), or
- the date of last follow-up date of the start of surveillance period +1 (for subjects who are non-cases).

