This methodology is based on the following. Assuming that the number of subjects who are cases in the INO-4800 group follows a Poisson distribution with parameter λ_v and the number of subjects who are cases in the placebo group follows a Poisson distribution with parameter λ_c , then conditional on total number of subjects with cases, t, the number of subjects who are cases in the INO-4800 group follows a binomial distribution with parameters (t, $p = \lambda_v/(\lambda_v + \lambda_c)$). The relationship between p and efficacy is: efficacy = (1-(1+k)p)/(1-p). Therefore, testing efficacy > 30% corresponds to testing p < 0.70/(0.70+k). Similarly, the confidence interval for efficacy is (1-(1+k)UB_p)/(1-UB_p), (1-(1+k)LB_p)/(1-LB_p), where UB and LB are the Clopper-Pearson upper and lower limits for the proportion.

The efficacy time frame is defined by symptoms beginning at any time starting from 14 days after Dose 2 and ending 12 months after Dose 2. Subjects identified as cases that started prior to this time point will be excluded. Subjects with multiple instances meeting the case definition will be counted only once, using the first such instance.

The PP population will be primary for the analysis of efficacy in this trial. Efficacy analysis using the mITT population will also be conducted counting cases from 14 days postdose 1 as a supportive analysis. The ITT population will also be used for a supportive analysis counting cases starting from randomization.

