9.3.4 COMPLIANCE WITH ELECTRONIC RECORDS/SIGNATURES REGULATIONS (21CFR PART 11)

INO-4800	COVID19-311
Inovio Pharmaceuticals, Inc.	Clinical Protocol

When applicable, this clinical trial is to be conducted in compliance with the regulations on electronic records and electronic signature.

9.3.5 **COMPLIANCE WITH PROTOCOL**

Subjects are not required to follow special instructions specific to the IP used in this clinical trial. Subjects will be provided with Investigator emergency contact information and advised to report all AEs. While every effort should be made to avoid protocol deviations, should an important deviation be discovered, the Sponsor must be informed immediately. Any protocol deviation impacting subject safety must be reported to the Medical Monitor immediately.

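### The primary per-protocol set excludes any subject with any protocol violation at any time, so a later outside COVID-19 vaccination removes valid earlier cases and person-time; VE is biased only if such exclusions depend on arm and case status together

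*Protocol*

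**What the plan says.** Section 8.4 defines the PP population as one that "includes all subjects who receive all doses of Study Treatments and have no protocol violations". For baseline-seronegative subjects, analyses on this set "will be primary for the analyses of efficacy in the Phase 3 segment of this trial", and Section 8.5.1 repeats: "The PP population will be primary for the analysis of efficacy in this trial". The definition has no importance threshold, no condition that the violation could affect efficacy, and no cut-off date. Section 9.3.5 does recognise a graver class ("should an important deviation be discovered, the Sponsor must be informed immediately"), but Section 8.4 does not use it. The term protocol violation is not defined.

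Three other provisions matter:

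- Section 6.4.7: "In the Phase 3 segment, subjects should not receive any other drug/vaccine intended as COVID-19 prophylaxis during the trial".
- Section 4.3 foresees that some subjects will be vaccinated elsewhere, and says "subjects should be requested to remain in the trial until the last visit".
- Section 8.5.1 ends a subject's follow-up time at first disease diagnosis or, for a non-case, at last follow-up. It does not stop the clock at a violation or an outside vaccination.

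Section 8.1 states that Section 8 contains the formal statistical analysis plan, so the rule is stated here and not deferred. The wording is the same in versions 1.0USA and 2.0USA. Only the closing pages of version 7.0 are available, so whether it kept the rule cannot be checked.

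**The concern.** Membership of the primary set can be decided by something that happens long after the endpoint. Take a subject who receives both doses, becomes a confirmed case in month 3 and takes a licensed vaccine in month 8. Read literally, Section 8.4 removes that subject, the case and all the person-time. A non-case vaccinated late in the year likewise loses all the time already observed. A case counted at the 75- or 112-case interim could be gone by the final analysis.

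This is selection on post-randomisation behaviour in the one analysis that decides success. At the least it loses valid information. At worst, if the people removed differ by arm and by case status together, the case split or the follow-up ratio k shifts, and VE, type I error and power shift with it.

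**Working it through.** **Inputs from the protocol.** 149 cases, null VE 30%, true VE 60%, final one-sided alpha 0.022 and point estimate above 50% (Sections 8.5.1, 8.5.6, 8.6); 4476 and 2238 seronegative subjects (Table 2), so k = 0.5; attack rate 3.7%. **Assumed:** all outside-vaccination rates, because the protocol gives none; and that such a vaccination counts as a violation, inferred from Section 6.4.7.

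**1. The plan's own figures.** The null proportion of cases on INO-4800 is 0.70/(0.70 + 0.5) = 0.5833; at VE 60% it is 0.40/(0.40 + 0.5) = 0.4444. With 149 cases the largest rejecting count is 74, where VE = 1 − 0.5 × 74/75 = 50.7%, so the point-estimate rule is also met. Final-look rejection is 2.0% under the null and 91.4% at VE 60% (2.2% and 91.6% over all three looks). Sample size: 149/[0.037 × (1/3 + 2/3 × 0.4)] = 6711.7, rounded up to a multiple of 3, 6714. These figures reproduce and are not in question.

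**2. Data lost.** Constant hazards over one year, 3.7% placebo attack rate, VE 60%, 20% outside uptake in both arms continuing after a case. Expected cases are 149.8 with no outside vaccination, 134.3 with censoring at vaccination, and 119.9 with whole-subject deletion. If nobody vaccinates after a case, both rules keep 134.3 cases, and deletion loses only person-time.

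**3. When VE is biased.** Let s be the share of cases kept in an arm and r the share of person-time kept (V for INO-4800, P for placebo). Then

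1 − VE(estimated) = (1 − VE) × (sV/rV)/(sP/rP).

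Equal uptake gives sV = sP and rV = rP, so there is no bias. Arm-different uptake that is the same in cases and non-cases gives s = r in each arm, so again there is none. Bias needs s/r to differ between arms, that is, joint dependence on arm and case status.

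**4. Size when no case vaccinates (s = 1).** Here r = 1 − uptake, k = 0.5 × (1 − uP)/(1 − uV), and the critical count is recomputed from Binomial(149, 0.70/(0.70 + k)). The case total stays at 149 because the trial is case-driven.

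| Uptake INO-4800 / placebo | k | Critical count | True VE | Estimated VE | Final-look rejection |
|---|---|---|---|---|---|
| equal | 0.500 | 74 | 30% | 30% | 2.0% |
| 20% / 22% | 0.488 | 75 | 30% | 31.8% | 3.0% |
| 20% / 23% | 0.481 | 75 | 30% | 32.6% | 3.0% |
| 15% / 25% | 0.441 | 78 | 30% | 38.2% | 8.2% |
| equal | 0.500 | 74 | 60% | 60% | 91% |
| 22% / 20% | 0.513 | 73 | 60% | 59.0% | 88% |
| 25% / 15% | 0.567 | 69 | 60% | 54.7% | 71% |

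Worked line, 15%/25%: 0.70 × 0.75/0.85 = 0.618, so VE is 38.2%. If cases there vaccinate at one quarter of the non-case rate, rejection is 6.0%. If they vaccinate at the same rate as non-cases, VE returns to 30% and rejection is 1.6%. In the 15%/25% row the point-estimate rule allows 79 INO-4800 cases, so it gives no protection.

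**5. Cross-check.** The constant-hazard model lets early vaccinators leave the risk set and is milder. A 10%/20% split with no case vaccinating gives 34.1% for a true 30% and 62.3% for a true 60%. The same split continuing unchanged after a case gives 30.0% and 60.0%. Censoring at outside vaccination returns the true VE in every scenario run, given vaccination independent of disease risk.

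**The case against.** The strongest reply is that bias needs two conditions together and that the design works against the first. Phase 3 is double-blind, both arms receive two injections with electroporation, and Section 5.2.1 declines unblinding to help a subject decide on another vaccine. A large arm gap in uptake is therefore unlikely, and a gap of 2 to 3 points is more plausible than 10. This stands, and it is why the small-gap rows carry the weight.

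The plan also has safeguards. "Subjects excluded from the PP population will be identified and documented prior to unblinding of the trial database", and mITT and ITT analyses are prespecified as supportive, so a PP result driven by exclusions should be visible. That is true but partial. Blinded listing prevents knowing selection, not selection on what subjects did after randomisation. The supportive analyses do not set the success criterion. They also start counting at other times (14 days after dose 1, and randomisation), and ITT treats missing case status as a case, so a difference from PP would be hard to attribute.

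It can also be said that violation may be meant more narrowly than any deviation. That is possible, but Section 8.4 does not say so.

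A reader might further infer that small slips across the many scheduled contacts would empty the PP set. The documents give no violation rate to support this. In a case-driven trial, lost cases would mean more enrolment or longer accrual, not necessarily a smaller final analysis.

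**Conclusion.** The defect is in the wording of Section 8.4, and it should be fixed. As written, and if outside vaccination counts as a violation, the primary analysis discards all earlier person-time of anyone vaccinated elsewhere, and any earlier case among them: about 120 against 134 cases kept under the assumed 20% uptake in both arms.

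A reader might infer that the primary VE is biased or that type I error is about 8%. The documents do not support that. No uptake rates are given, and neither equal uptake nor an arm difference shared by cases and non-cases produces bias. With small gaps and no case vaccinating, a true VE of 30% reads as 32–33%, with rejection about 3.0% instead of 2.0%; a reverse gap (22%/20%) takes power from 91% to 88%. The 38%, 8.2% and 71% results belong to an extreme 10-point gap. The sample size and boundaries are not in error. The conclusion applies to versions 1.0USA and 2.0USA.

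**What to change.** In Section 8.4, define PP as subjects who received both doses and had none of a short list, fixed while blinded, of important deviations that affect efficacy and occur before surveillance starts (14 days after dose 2). In Section 8.5.1, state that a later such event, for example an outside COVID-19 vaccination, censors follow-up on its date and never removes a case whose symptoms began earlier. Check whether version 7.0 already does this.

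The cost is wording, a blinded deviation list and some programming. No additional subjects or data are needed: outside vaccinations and their dates are already recorded as concomitant medication (Sections 4.3 and 6.4.6). The downside is that censoring assumes outside vaccination is independent of disease risk, so the mITT and ITT analyses should be kept as sensitivity analyses.

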8.5.1 PRIMARY ANALYSIS

Phase 2 Segment

Post-baseline increases from baseline in interferon-γ ELISpot response magnitudes will be compared between treatment groups using differences in medians and associated non-parametric 95% CIs.

INO-4800	COVID19-311
Inovio Pharmaceuticals, Inc.	Clinical Protocol

Post-baseline increases from baseline in neutralizing antibody response titers will be compared between treatment groups using ratios of geometric mean fold-rises and associated t-distribution based 95% CIs.

The summaries listed above will be stratified according to NP positive/negative status and according to prior receipt of any non-study prophylactic COVID-19 vaccine of the subjects. Valid samples for statistical analysis purposes will be those collected: at least 6 and no more than 30 days after Dose 2 for the Week 6 timepoint; at least 174 and no more than 198 days after Dose 2 for the Week 30 timepoint; and at least 356 and no more than 380 days after Dose 2 for the Week 56 timepoint. Baseline is defined as the last measurement prior to the first treatment administration.

The PP population will be used for these immunogenicity analyses.

Phase 3 Segment

Among subjects who are SARS-CoV-2 seronegative at baseline, the primary hypothesis of relative efficacy greater than 30% will be tested with H_0 : $p \ge 0.70/(0.70+k)$ vs. H_1 : p < 0.70/(0.70+k), where p is the true proportion of subjects with disease who receive INO-4800 relative to the total number of subjects with disease, and k is the total amount of follow-up time in the placebo group divided by the total amount of follow-up time in the INO-4800 group.

A p-value for this hypothesis test and corresponding confidence interval will be computed based on the exact binomial method of Clopper-Pearson. Success will be concluded if the one-sided p-value is <0.022 and the corresponding lower bound of the two-sided 95.6% Cl for efficacy exceeds 30% (alpha-level adjusted for interim analyses, see Section 8.5.6), and the point estimate for efficacy exceeds 50%.

For calculating k, an individual subject's follow-up time is either:

- the date of first disease diagnosis date of the start of surveillance period +1 (for subjects who are cases), or
- the date of last follow-up date of the start of surveillance period +1 (for subjects who are non-cases).

This methodology is based on the following. Assuming that the number of subjects who are cases in the INO-4800 group follows a Poisson distribution with parameter λ_v and the number of subjects who are cases in the placebo group follows a Poisson distribution with parameter λ_c , then conditional on total number of subjects with cases, t, the number of subjects who are cases in the INO-4800 group follows a binomial distribution with parameters (t, $p = \lambda_v/(\lambda_v + \lambda_c)$). The relationship between p and efficacy is: efficacy = (1-(1+k)p)/(1-p). Therefore, testing efficacy > 30% corresponds to testing p < 0.70/(0.70+k). Similarly, the confidence interval for efficacy is (1-(1+k)UB_p)/(1-UB_p), (1-(1+k)LB_p)/(1-LB_p), where UB and LB are the Clopper-Pearson upper and lower limits for the proportion.

The efficacy time frame is defined by symptoms beginning at any time starting from 14 days after Dose 2 and ending 12 months after Dose 2. Subjects identified as cases that started prior to this time point will be excluded. Subjects with multiple instances meeting the case definition will be counted only once, using the first such instance.

The PP population will be primary for the analysis of efficacy in this trial. Efficacy analysis using the mITT population will also be conducted counting cases from 14 days postdose 1 as a supportive analysis. The ITT population will also be used for a supportive analysis counting cases starting from randomization.

